### **3. Participating Institutions**

Participants for this study will be recruited from the patient population evaluated and treated at the [REDACTED]. Members of the CINJOG network may also participate in [REDACTED] study, and patients may be evaluated and treated at these respective institutions as well.

### **4. Experimental Design and Methods**

Eligible patients with rising PSA after definitive therapy of localized prostate cancer, no visible metastatic disease on conventional imaging studies including CT scan of the abdomen and pelvis and bone scan, and a PSA doubling time of greater than 6 cycles will be treated with 4 cycles of metformin 500mg/1000mg BID and aspirin 81mg/day.

#### **4.1 Disease Assessment After Run In Stage:**

After 4 cycles of treatment patients with disease progression (PSA increase of >50% and minimum of 2ng/ml rise in PSA) will come off study. Patients with disease response (>25% decline in PSA) will continue on study agents.

Patients with stable disease (not meeting criteria for progression or stable disease) will be randomized to continue on the study regimen or receive placebo therapy for 6 cycles.

#### **4.2 Run In Stage Treatment:**

Metformin treatment will be started at 500 mg twice daily, if no GI toxicity grade greater than 1 is noted after 2 weeks it will be increased to 500 mg with breakfast/1000 mg at bedtime, which is the target dose for the remainder of the study. Aspirin 81 mg will be taken once daily with food.

#### **4.3 Randomization Stage Treatment:**

Patients meeting criteria for randomization will be randomized to continue therapy with metformin 500 mg in the morning and 1000 mg at night and aspirin 81 mg per day and or to placebo metformin and, placebo aspirin.

Randomization will be performed based on a randomization schedule generated by statistician ([name]) using a stratified randomization method in order that the numbers of obese patients (BMI  $\geq$  30) on each group are balanced.

Protocol Version 8.0 12/01/2017

Title: A Phase 2 Randomized Discontinuation Trial in Patients with Hormone-Dependent Rising Prostate-Specific Antigen Progression After Local Therapy for Prostate Cancer Evaluating the Synergy of Metformin Plus Aspirin (PRIMA Trial).

PI: [REDACTED]

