28 PATIENTS PER ARM**

**STATISTICAL ANALYSIS:** With 28 patients randomized to treatment or placebo the study will have 80% power to detect an increase in the proportion of patients with progression at 6cycles from 40% to 80% with alpha =0.05

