## **16.2 Outcome Measures**

Difference in the stable PSA rates after 6 cycles of metformin and aspirin or placebo therapy will be calculated in patients who have received 4 cycles of open label treatment during the “run in phase”

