## **16.3 Sample Size and Statistical Analysis**

In this study, we hypothesize that patients with stable PSA after 4 cycles of open label treatment who are then treated with 6 cycles of metformin and aspirin will have a 40% rate of PSA or clinical progression compared to 80% rate of progression in patients treated with placebo. With 28 patients randomized to treatment or placebo the study will have 80% power to detect an increase in the proportion of patients with progression at 6 cycles from 40% to 80% with alpha =0.05. Assuming that approximately 10 patients progress prior to randomization, a total of 66 patients will be entered on this study.

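### Randomisation is stratified by obesity (BMI ≥ 30) but the analysis section does not carry that stratum forward; if BMI predicts progression, an unstratified test would be valid but somewhat conservative

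*Combined protocol and SAP*

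**What the plan says.** Section 4.3 says the randomisation schedule is generated "using a stratified randomization method in order that the numbers of obese patients (BMI" ≥ 30) are balanced between the groups. No other stratification factor is named.

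Section 16.2 gives the outcome comparison: "Difference in the stable PSA rates after 6 cycles of metformin and aspirin or placebo therapy will be calculated". Section 16.3 assumes a "40% rate of PSA or clinical progression compared to 80% rate of progression in patients treated with placebo". For that assumption it claims a power of 80%, the target being a rise in "progression at 6 cycles from 40% to 80% with alpha =0.05". The synopsis confirms "28 PATIENTS PER ARM".

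Neither section names a test, its sidedness, a stratified analysis or an adjustment for BMI, and no other section supplies one. The expected share of obese men is not given, and nothing says how strongly obesity predicts progression.

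**The concern.** When randomisation balances a factor that predicts outcome, the arm difference varies less from trial to trial than an unstratified standard error implies. A test that ignores the factor then rejects less often than its nominal level and can lose power. Obesity is the only factor the sponsor chose to balance, and section 1.2.2 lists serum biomarkers linked to obesity as a secondary aim, so it is natural to ask why the factor stops at the randomisation step.

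At stake is a modest amount of efficiency in a trial of 56 randomised men. There is also an open choice: with no test named, whether to stratify could be decided after the data are seen.

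**Working it through.** **1. Reproduce the plan's figure.** Inputs from 16.3: p₁ = 0.40, p₂ = 0.80, α = 0.05, power 80%. Two-sided is assumed because sidedness is not stated. The mean rate is 0.60.

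- Uncorrected: n = [1.960·√(2·0.6·0.4) + 0.842·√(0.4·0.6 + 0.8·0.2)]² / 0.4² = (1.358 + 0.532)² / 0.16 = 22.3, so 23 per arm.
- Continuity-corrected: n′ = (22.33/4)·[1 + √(1 + 4/(22.33·0.4))]² = 5.58·(2.203)² = 27.1, so 28 per arm.

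The stated 28 is therefore what a two-sided, continuity-corrected comparison without stratification requires. Exact power at 28 per arm is 88.2% for Pearson chi-square, 82.3% for Fisher and 80.8% for Yates. All three reach 80%.

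**2. The mechanism, by hand.** Take 14 obese and 14 non-obese men per arm, a common progression rate of 60% in both arms, and a BMI odds ratio of 6. The stratum rates are then 40% and 80%: the odds are 0.667 and 4, with ratio 6 and mean rate 60%. The unstratified variance per man is 0.6·0.4 = 0.24. The mean within-stratum variance is (0.24 + 0.16)/2 = 0.20. The standard error is overstated by √(0.24/0.20) = 1.095, so the effective critical value is 1.96·1.095 = 2.15, and the two-sided error is about 3.2% instead of 5%.

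**3. Size over a range.** Assumptions not in the documents: 6, 8, 11 or 14 obese men of 28 in each arm (21% to 50%), exactly balanced; the same BMI odds ratio in both arms; marginal rates held at 40%/80% for power and 60%/60% for type I error. I summed the binomial probabilities of every possible outcome for which each uncorrected two-sided test rejects at |z| ≥ 1.96. Here z is (X − Y)/n divided by √(2p(1 − p)/n) for chi-square, where X and Y are the numbers progressing in the two arms and p is the pooled rate. For CMH, z is Σ(x − E)/√ΣV over the two strata.

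| BMI odds ratio | Type I error, chi-square | Type I error, CMH | Power, chi-square | Power, CMH | Change in power (points) |
|---|---|---|---|---|---|
| 1 | 4.8% | 4.5% | 88.2% | 87.6–87.7% | −0.6 |
| 2 | 4.5–4.6% | 4.5–4.7% | 88.4–88.5% | 88.2–88.7% | −0.2 to +0.2 |
| 3 | 4.0–4.4% | 4.6–4.9% | 88.6–88.9% | 88.9–90.1% | +0.3 to +1.2 |
| 6 | 3.0–3.9% | 4.9–5.1% | 89.1–89.8% | 90.7–92.9% | +1.5 to +3.1 |

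**4. Continuity-corrected versions.** Going from Yates to corrected CMH, power changes from 80.8% to about 81.1% at an odds ratio of 1, and from 81.7–82.3% to 84.9–87.6% at 6. So corrected CMH gives about 81% to 88% over this range and also meets the stated 80%.

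**The case against.** The case for leaving the plan alone is strong in several respects.

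- **The documents do not show that BMI predicts progression.** Section 4.3 gives balance as its only reason, and stratified randomisation already delivers balance. The background also says the run-in is meant to yield a more homogeneous group for randomisation, which makes a large remaining BMI effect less obvious. This stands: up to an odds ratio of about 2, stratifying recovers essentially nothing and may cost a fraction of a point.
- **The plan does not commit to an unstratified test.** A reader might infer that it does, because 28 per arm matches an unstratified formula. But no test is named, and a corrected CMH test at 28 per arm also gives about 81% power with no BMI effect. This stands: the gap is an omission, not a wrong test.
- **Most of the apparent gain comes from elsewhere.** Setting CMH against Fisher's test shows a gain of 5 points or more, which a reader might credit to stratifying. Going from Fisher to unstratified chi-square already adds 88.2 − 82.3 = 5.9 points when BMI has no effect. Fisher's type I error of 2.6% in that case comes from its own discreteness. None of this is evidence about BMI.

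The objection does not remove the reason to settle the point in advance. Matching the analysis to the randomisation costs little and closes one choice that could otherwise follow the data.

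**Conclusion.** This is a minor specification gap and an opportunity for improvement, not a validity error. The factor used to randomise is missing from the analysis. If BMI is prognostic, ignoring it makes the test conservative, never liberal. The effect is negligible at an odds ratio of 2 and reaches 1.5 to 3.1 points of power at 6. The obese share and the odds ratios are assumptions throughout.

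Two stronger readings are not supported. First, a reader might conclude that the trial gives up power or is too small. The loss depends on a BMI effect that the documents do not give, and 28 per arm reaches the stated 80% with or without stratifying. Second, a reader might want the power restated as 87% to 92%. The upper end needs a BMI odds ratio near 6 and an assumed obese share, and the whole range relies on dropping the continuity correction that the stated sample size reflects.

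**What to change.** In section 16.3, name the primary test as a two-sided Cochran-Mantel-Haenszel test at α = 0.05, stratified by BMI category (below 30, or 30 and above) as randomised. State whether a continuity correction is used. Report a stratum-weighted risk difference with a 95% CI. If the strata are exactly balanced, Mantel-Haenszel weights return the same point estimate as the plain difference, and only the standard error changes. Leave the statement of 80% power at 28 per arm as it is.

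The cost is one or two sentences. No new data are needed, because the stratum has to be known to randomise each man. The statistical downside is a loss of less than 0.7 points of power (88.2% to about 87.6%, uncorrected) if BMI turns out not to be prognostic.

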In patients with rising PSA, drugs causing disease stabilization would be expected to lead to a slowing in the rate of rise in the PSA, which can also be expressed as a lengthening of the PSA doubling time. Multiple prior phase II trials for men with rising PSA, including several randomized placebo controlled trials, have assessed changes in PSA doubling time as an endpoint. In these trials it was noted that patients in the placebo arm often have an increase in the PSADT after going on study. As noted by Paller et al., in a Rosiglitazone trial involving 106 patients, 73% of patients on placebo had an increase of PSADT in excess of 100%, and 31% exceeded 200% in PSADT lengthening. In an Atrasentan trial involving 222 patients, 78% of the patients on placebo had a lengthening of PSADT. In a celecoxib trial involving 78 patients, 20% of the patients on placebo had >200% increase of PSADT. In these studies, the increase in pre and on-treatment PSA doubling time has been attributed to difference between spacing interval and number of PSA values collected in an uncontrolled “pre-study period compared to the regular intervals at which PSA values are collected once on study”.

In the current design all subjects will receive study therapy for 4 cycles. During this period PSA will be measured at monthly intervals in order to determine a PSA doubling time in a uniform manner, and to obtain a relatively homogeneous population of patients for randomization. Patients

Protocol Version 8.0 12/01/2017

Title: A Phase 2 Randomized Discontinuation Trial in Patients with Hormone-Dependent Rising Prostate-Specific Antigen Progression After Local Therapy for Prostate Cancer Evaluating the Synergy of Metformin Plus Aspirin (PRIMA Trial).

PI: [REDACTED]

meeting the study specified definition of stable disease will then proceed to randomization while patients meeting criteria for PSA progression will come off study and those patients with PSA response will continue on therapy until the study definition of disease progression is met.

After the run in phase patients meeting the criteria for stable disease will be randomized to continue therapy with metformin and aspirin or to placebo metformin, and placebo aspirin.

The secondary objective of this study is to determine whether the intervention may modify the PSA levels and the serum obesity-related PCa biomarkers. The tolerability of and compliance of metformin and aspirin treatment in these subjects will also be evaluated.

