#### **4.5 Disease Progression Criteria During Randomization Stage Treatment**

Disease progression during the randomization is defined as rise in PSA by >50% above baseline and absolute increase of 2ng/mL or radiographic progression

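### The primary comparison names no test or covariate; adjusting for PSA at randomisation, which decides who can progress below 4 ng/mL, should be pre-specified

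*Combined protocol and SAP*

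**What the plan says.** - **Randomisation (4.3).** Stable men are randomised "using a stratified randomization method in order that the numbers of obese patients" are balanced between the arms. BMI of 30 or more is the only factor named.
- **Outcome (16.2).** "Difference in the stable PSA rates after 6 cycles of metformin and aspirin or placebo therapy will be calculated". No test, model or covariate follows.
- **Sample size (16.3 and synopsis).** "28 PATIENTS PER ARM"; "the study will have 80% power to detect an increase in the proportion of patients with progression at 6 cycles from 40% to 80" percent, "with alpha =0.05". Sidedness is not stated.
- **Progression after randomisation (4.5).** "rise in PSA by >50% above baseline and absolute increase of 2ng/mL or radiographic progression". The synopsis has the same two PSA conditions.
- **Entry PSA (5.1.3).** At least 0.2 ng/mL after surgery, with or without radiation; at least 2.0 ng/mL above nadir after radiation alone. Doubling time must exceed 4 months (section 4 says 6 cycles).
- **PSA on file (section 6).** The schedule has a PSA in the randomisation column (footnote 8). Footnote 1 separately calls the PSA taken before C1D1 the baseline for assessing response.

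**The concern.** A rule that demands both a relative and an absolute rise is harder to meet from a low PSA. Surgical patients may enter at 0.2 ng/mL, so the randomised group can mix men for whom a 50% rise suffices with men who would need a three-fold or larger rise. BMI stratification does not balance that mix. With 28 men per arm, a chance difference in it could mask or mimic a drug effect, and an unadjusted comparison leaves that variation in the error. The value needed to adjust is already collected. Since no primary test is written down, one has to be added anyway, and a PSA term chosen after unblinding would be open to challenge.

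**Working it through.** **1. The plan's own figure.** Two-sided alpha 0.05 (assumed), power 0.80, rates 0.40 and 0.80, mean rate 0.60.

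Uncorrected: n' = [1.960·√(2·0.6·0.4) + 0.842·√(0.4·0.6 + 0.8·0.2)]² / 0.4² = 22.3, so 23.

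Continuity-corrected: n = (n'/4)·[1 + √(1 + 4/(n'·0.4))]² = 27.1, so 28.

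The stated 28 per arm is reproduced by an unadjusted formula with no PSA term. At 28 per arm, power is 82.3% (exact two-sided Fisher) or 88.5% (uncorrected pooled z). The total also agrees: 56 + 10 = 66.

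**2. What the progression rule requires.** Taking the randomisation PSA as baseline, the two conditions meet where 0.5·PSA = 2, at 4 ng/mL. Below that the required fold rise is 1 + 2/PSA; at or above it, 1.5. Six 4-week cycles are 168 days, or 168/30.4375 = 5.52 months. The longest doubling time that still reaches the rule is 5.52 / log2(fold rise).

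| PSA at randomisation (ng/mL) | Fold rise needed | Longest doubling time (months) |
|---|---|---|
| 0.2 | 11 | 1.6 |
| 0.5 | 5 | 2.4 |
| 1 | 3 | 3.5 |
| 1.25 | 2.6 | 4.0 |
| 2 | 2 | 5.5 |
| 4 or more | 1.5 | 9.4 |

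Under steady growth with a doubling time above 4 months, a man below about 1.25 ng/mL cannot reach PSA progression by 6 cycles on either arm. Under the section 4 criterion (above 6 cycles) the limit is 2.0 ng/mL. Radiographic progression would still count.

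If baseline in 4.5 means the pre-C1D1 value, the span is 40 weeks (280/30.4375 = 9.20 months) and the limit, on that earlier PSA, is 2/(2^(9.20/4) − 1) = 0.51 ng/mL. The definition therefore matters.

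**3. Chance imbalance.** If 30% of men are below 4 ng/mL (assumed), the binomial probability that the arms differ by 6 or more such men (6/28 = 21 points) is 11%; if 50% are, 14%.

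**4. Simulated power, 28 per arm.** Everything about the PSA distribution here is assumed: lognormal PSA, untreated median doubling time 5.5 months (SD of log growth 0.4) truncated to above 4 months, 10% assay noise, run-in selection by 4.1, PSA every 4 weeks; 1,500 trials per row. The drug multiplies the growth rate by the factor shown. Adjusted means a likelihood-ratio logistic test with log PSA; CMH is Cochran-Mantel-Haenszel split at the median PSA.

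| Median PSA (SD of log) | Factor | Progression, placebo / drug | Below 4 ng/mL | Chi-square | Adjusted | CMH |
|---|---|---|---|---|---|---|
| 1.5 (1.2) | 0.5 | 41% / 11% | 75% | 75.9% | 94.3% | 88.6% |
| 1.5 (1.2) | 0.65 | 42% / 21% | 75% | 41.3% | 66.5% | 59.6% |
| 3 (1.0) | 0.5 | 63% / 18% | 54% | 93.6% | 98.5% | 98.2% |
| 3 (1.0) | 0.65 | 63% / 35% | 55% | 57.1% | 78.4% | 71.3% |
| 5 (0.8) | 0.5 | 80% / 26% | 31% | 99.1% | 99.7% | 99.7% |
| 5 (0.8) | 0.65 | 79% / 47% | 30% | 71.0% | 78.5% | 73.1% |
| 10 (0.6) | 0.5 | 90% / 32% | 3% | 99.9% | 99.9% | 99.9% |
| 10 (0.6) | 0.65 | 89% / 55% | 3% | 82.5% | 83.9% | 80.5% |

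A separate simulation gave gains over chi-square of 12 points at median PSA 2, 6 at 4, 2 at 6 and about 0 at 10.

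For predicting progression on placebo, the AUC of PSA was 0.94 at median 1.5, 0.76–0.78 at median 5 and 0.56–0.57 at median 10; that of growth rate was 0.67–0.68, 0.82–0.83 and 0.95.

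**5. Type I error.** Likelihood-ratio logistic test: 4.9–6.0% with log PSA alone, 5.9–7.1% with a BMI term added. CMH: 4.2–5.1%.

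**The case against.** - **The plan does not choose an unadjusted analysis.** A reader might infer from 16.2 that PSA is deliberately left out. The documents do not support that: no test or covariate is named, and only the sample-size arithmetic is unadjusted. This stands. The defect is an unspecified method, and the PSA term belongs in the text that repairs it.
- **PSA is not a dominant predictor in general.** This stands. At 4 ng/mL or above the required rise is 1.5-fold whatever the level, and growth rate predicts better. The 0.2 ng/mL floor applies only after surgery; men after radiation alone enter at 2 ng/mL or more. It is also an entry value, not the PSA after run-in.
- **The gain is small near the planned rates.** Largely right. With a median of 10 (SD 0.8), the drug halving growth and an untreated median doubling time of 6 months, rates were 77% and 31% and there was no gain. At 79% and 47% in the table, the gain was 7.5 points adjusted and 2.1 by CMH. An 80% placebo rate is itself hard to square with many low-PSA men.
- **Part of the apparent gain is test size.** Fair: the likelihood-ratio test runs above 5%, and Fisher runs at about 3%. That rules out a plain likelihood-ratio test, not adjustment.
- **Adjustment does not make low-PSA men informative.** True. Those who cannot reach a 2 ng/mL rise contribute little on either arm; that is a property of the endpoint.

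**Conclusion.** The point holds in a limited form. From the documents alone: BMI is the only stratum, no test or covariate is stated, 28 per arm matches an unadjusted comparison, and the progression rule ties the chance of PSA progression to PSA level below 4 ng/mL but not above. The 1.25 ng/mL limit rests on steady growth, a doubling time above 4 months and the randomisation PSA as baseline.

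The size of the gain cannot be derived from the documents. Over the assumed distributions it runs from about 0 where nearly all men are at or above 4 ng/mL, through roughly 5 to 12 points where many are below, to about 25 points in the most favourable setting. Settings near the planned rates gave about 0 to 8 points.

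A reader might conclude that the trial is underpowered or certain to lose power. That does not follow: if 40% and 80% are true, an unadjusted test meets the planned 80%. The case for acting is that a pre-specified term is cheap, protects against chance imbalance, and has to be fixed before unblinding.

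**What to change.** 1. **First reconcile the baseline.** State whether baseline in 4.5 is the randomisation PSA (footnote 8) or the pre-C1D1 PSA (footnote 1). The doubling-time criteria in section 4 and 5.1.3 also need reconciling.
2. **Name the primary test in 16.3.** Adjust for the BMI stratum and one PSA term at randomisation: log PSA, or a split at 4 ng/mL. Use a method that holds its level with 56 men, such as a Cochran-Mantel-Haenszel or stratified permutation test, or Firth logistic regression once its type I error has been checked by simulation. State the sidedness.
3. **Report** the stratified or standardised risk difference with its confidence interval, and keep the crude comparison as a sensitivity analysis.

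Cost: one paragraph of text and slightly more analysis work; no added patient, visit or sample. The downsides are small. CMH lost 2 points (82.5% to 80.5%) in one setting where almost every man was above 4 ng/mL, and a plain likelihood-ratio logistic test should be avoided because it runs at about 6–7%.

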#### **4.4 PSA Responder Treatment:**

Patients meeting criteria for PSA response (>25% decline in PSA during the run-in phase) randomization will be assigned to continue therapy with metformin 500 mg in the morning and 1000 mg at night, and aspirin 81 mg per day until disease progression.

#### **4.5 Disease Progression Criteria During Randomization Stage Treatment**

Disease progression during the randomization is defined as rise in PSA by >50% above baseline and absolute increase of 2ng/mL or radiographic progression

#### **4.6 Duration of Follow-up**

For this protocol, all patients, including those who discontinue protocol therapy early, will be followed for response (or progression) and for survival for 1 year from the date of registration. All patients must also be followed through completion of all protocol therapy.

### **5. Patient Selection Criteria**

#### **5.1 Inclusion Criteria**

A patient is eligible for enrollment if all of the following inclusion criteria are met:

- 5.1.1 Patients with histologically proven prostate cancer treated with surgery, radiation, or the combination of surgery and radiation or prostate cancer (metastatic to regional lymph nodes) with resection of the nodes, who now has a rising PSA value after definitive local therapy, and no visible metastatic disease on conventional imaging studies
- 5.1.2 Patients must have undergone local treatment via prostatectomy or radiation therapy.
- 5.1.3 Patients must have PSA progression after local treatment:
  - a. PSA values for patients after surgery (or surgery and salvage/adjuvant radiation) must be greater than or equal to 0.2 ng/mL, determined by two measurements, at least 1 month apart and at least 6 months after prostatectomy

**OR**

- b. PSA values for patients after radiation must be greater than or equal to 2.0 ng/ml greater than the nadir achieved after radiation, determined by two measurements at 1 month apart and at least 6 months after the radiation treatment is completed. (Patients who received adjuvant or salvage radiation after prostatectomy must have PSA of greater than or equal to 0.2)
- c. The first two PSA values (in 5.1.3a or 5.1.3b), along with a third (pre-study) value must all be rising (i.e., there must be an overall rising trajectory, such that the third value cannot be lower than the first value).
- d. PSA doubling time using the mkscc.org PSA doubling time calculator must be greater than 4 months

5.1.4 Baseline bone scan, chest x-ray and CT/MRI of abdomen/pelvis demonstrating no metastatic disease.

Protocol

Approval Date: [REDACTED]  
Expiration Date: [REDACTED]

1/15/2020

Title: A Phase 2 Randomized Discontinuation Trial in Patients with Hormone-Dependent Rising Prostate-Specific Antigen Progression After Local Therapy for Prostate Cancer Evaluating the Synergy of Metformin Plus Aspirin (PRIMA Trial).

PI: [REDACTED]

- 5.1.5 A bone scan and a CT or MRI abdomen/pelvis and chest x-ray (CXR) or chest CT scan, will have been performed within 12 weeks of treatment start. Radiographic assessments will be selected by the attending physician as clinically indicated.
- 5.1.6 Age  $\geq$  18 years
- 5.1.7 Estimated life expectancy of at least 6 months.
- 5.1.8 ECOG performance status  $\leq$  2. (see Appendix A)
- 5.1.9 A WBC  $>$  3500/ $\mu$ l, ANC  $>$  1500/ $\mu$ l, hemoglobin  $>$  10 g/dl, and platelet count  $>$  100,000/ $\mu$ l are required.
- 5.1.10 Adequate renal function with estimated GFR by Cockcroft Gault of greater than 40 ML per minute
- 5.1.11 Total bilirubin must be within 1.5X the normal institutional limits. If total bilirubin is outside the normal institutional limits, assess direct bilirubin. The direct bilirubin must be within normal parameters. Transaminases (SGOT and/or SGPT) must be less than 2.5X the institutional upper limit of normal.
- 5.1.12 Patients must have a serum total testosterone level  $\geq$  150 ng/dL at the time of enrollment within 12 weeks prior to randomization.
- 5.1.13 Patients must sign informed consent.

